#### 6.4 Treatment/Follow-up Decision at Evaluation of Patient

- 6.4.1 Patients who have not had systemic disease progression and have experienced acceptable toxicity will be eligible for re-treatment at their current dose level until disease progression, unacceptable toxicity, or refusal.
- 6.4.2 Those patients who have not progressed and who have experienced unacceptable toxicity may be eligible for re-treatment at a lower dose. See Section 7.
- 6.4.3 Patients randomized to the alisertib alone arm that progress may begin treatment with fulvestrant and alisertib if the conditions listed in Section 6.1 are met.

Patients who are not eligible to continue on to fulvestrant plus alisertib or who choose not to continue on to fulvestrant plus alisertib will proceed to the Event Monitoring phase where patients will be followed every 6 months until death or a maximum of 5 years post-randomization for disease progression and death information.

Patients who proceed with fulvestrant plus alisertib treatment will continue until: disease progression, patient request, intolerability, or refusal.

- 6.4.4 Criteria for discontinuation of all protocol therapy include:
- Tumor progression during combination treatment with fulvestrant and alisertib
  - Arm 1 only: tumor progression during alisertib and patient will not be switching to combination treatment with fulvestrant and alisertib
  - Request by the patient to withdraw from all protocol treatment
  - Unacceptable adverse events
  - Treatment delay of >21 days (exception: recovery from Cycle 1 Day 15 severe neutropenia where treatment delay of >30 days triggers treatment discontinuation [see Section 7.3])
  - Intercurrent illness which would, in the judgment of the investigator, affect assessments of clinical status to a significant degree that require discontinuation of drug
  - Administration of radiotherapy, non-protocol chemotherapy, or an experimental drug during the trial

Patients who discontinue treatment for any of the above reasons will go to event monitoring. Once a patient has entered the event monitoring phase of the trial, his/her therapy is at the discretion of the treating physician.

- 6.4.5 If an eligible patient refuses treatment following registration (and is classified as a “cancel” by the Research Base), all on-study materials must be submitted to the Research Base.

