## 7. EXPECTED TOXICITIES AND DOSING DELAYS/DOSE MODIFICATIONS

### 7.1 Dose Modification Based on Adverse Events

- 7.1.1 Dose modifications based on Adverse Event documented prior to each cycle of treatment. Strictly follow the modification in the table provided below until individual treatment tolerance can be ascertained. If multiple adverse events occur, administer the dose based on the greatest dose reduction required for any single adverse event observed. Dose modifications apply to the treatment given in the preceding cycle and are based on adverse events observed in the prior dose.
- 7.1.2 Note that fulvestrant administration is not modified for any adverse event.
- If alisertib is held due to toxicity then fulvestrant should also be held. Both agents should be restarted together.
  - If alisertib is discontinued due to intolerability then fulvestrant is also discontinued.
- 7.1.3 If treatment is held greater than 21 days without resolution of any adverse events other than severe neutropenia or a 3rd dose reduction is required then study treatment is to be discontinued\* and the patient will enter the Event Monitoring phase of the study.(see Section 14.0).  
\*Note: If patient is deriving benefit from study treatment and the event can be managed safely, consult Study Chair ([name]) regarding continuation.
- 7.1.4 Dose reduction levels

Dose Level	Alisertib (twice daily) Days 1-3, 8-10, 15-17
-1	40 mg
-2	30 mg

→ → Use the NCI Common Terminology Criteria for Adverse Events (CTCAE) version 4.0\* unless otherwise specified ← ←

\* Located at [REDACTED]

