Investigations	Neutrophil Count Decreased Grade 3 (neutrophils <1000 - 500 cells/mm  )	
First Episode: Hold alisertib administration and check neutrophil counts within 5-7 days of report of Grade 3 ANC (referred to as ANC recheck #1).
 
(a) results of ANC recheck #1
 
 
- If neutrophils ≥1500 cells/mm^3, resume alisertib at current dose
 
- If neutrophils <1500 cells/mm^3, continue to hold alisertib and re-check neutrophils counts again within the next 7 days but at most 14 days after the first report of Grade 3 ANC (ANC recheck #2)
 
 
(b) results of ANC recheck #2
 
 
▪ If neutrophils ≥1500 cells/mm^3, resume alisertib at one dose lower
 
▪ If neutrophils remain <1500 cells/mm^3 14 days after first report of Grade 3 ANC, discontinue study treatment* 

 
Second Episode: Hold alisertib administration and check neutrophil count within 5-7 days of report of Grade 3 ANC (referred to as ANC recheck #1).
 
(a) results of ANC recheck #1
 
 
- If neutrophils ≥1500 cells/mm^3, resume alisertib at first dose level below current dose level
 
- If neutrophils <1500 cells/mm^3, continue to hold alisertib and re-check neutrophils counts again within the next 7 days but at most 14 days after the first report of Grade 3 ANC (ANC recheck #2)
 
 
(b) results of ANC recheck #2
 
 
▪ If neutrophils ≥1500 cells/mm^3, resume alisertib at first dose level below current dose
 
▪ If neutrophils remain <1500 cells/mm^3 14 days after first report of Grade 3 ANC in this second episode, discontinue study treatment* 

 
Third Episode: discontinue study treatment (see note*)
 
*NOTE: If patient is deriving benefit from study treatment and event can be managed safely, consult Study Chair regarding continuation.

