Investigations	Neutrophil count decreased Grade 4 (neutrophils <500 cells/mm  )	
First Episode: Hold alisertib administration and check neutrophil counts within 5-7 days of report of Grade 4 ANC (referred to as ANC recheck #1).
 
(a) results of ANC recheck #1
 
 
▪ If neutrophils <math>\geq 1500</math> cells/mm^3, resume alisertib at first dose level below at current dose
 
▪ If neutrophils <1500 cells/mm^3, continue to hold alisertib and re-check neutrophils counts again within the next 7 days but at most 14 days after the first report of Grade 4 ANC (ANC recheck #2)
 
 
(b) results of ANC recheck #2
 
 
▪ If neutrophils <math>\geq 1500</math> cells/mm^3, resume alisertib at first dose level below at current dose
 
▪ If neutrophils remain <1500 cells/mm^3 14 days after first report of Grade 4 ANC, discontinue study treatment* 

 
Second Episode: Hold alisertib administration and check neutrophil counts within 5-7 days of report of Grade 4 ANC results of ANC recheck #1
 
(a) results of ANC recheck #1
 
 
▪ If neutrophils <math>\geq 1500</math> cells/mm^3, resume alisertib at first dose level below current dose
 
▪ If neutrophils <1500 cells/mm^3, continue to hold alisertib and re-check neutrophils counts again within the next 7 days but at most 14 days after the first report of Grade 4 ANC (ANC recheck #2)
 
 
(b) results of ANC recheck #2
 
 
▪ If neutrophils <math>\geq 1500</math> cells/mm^3, resume alisertib at first dose level below at current dose
 
▪ If neutrophils remain <1500 cells/mm^3 14 days after first report of Grade 4 ANC, discontinue study treatment* 

 
Third Event: Discontinue study treatment (see note*)
 
*NOTE: If patient is deriving benefit from study treatment and event can be managed safely, consult Study Chair regarding continuation.

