Investigations	Platelet count decreased Grade 3 (25,000 – 50,000 cells/mm  )	
First Episode: Hold alisertib administration and check neutrophil counts within 5-7 days of report of Grade 3 PLT (referred to as PLT recheck #1)
 
(a) results of PLT recheck #1
 
 
▪ If platelets <math>\geq 100,000</math> cells/mm^3, resume alisertib at current dose
 
▪ If platelets <math>< 100,000</math> cells/mm^3, continue to hold alisertib and re-check platelet count again within the next 5- 7 days but at most 14 days after the first report of Grade 3 ANC (ANC recheck #2)
 
 
(b) results of PLT recheck #2
 
 
▪ If platelets <math>\geq 100,000</math> cells/mm^3, resume alisertib at first dose level below at current dose
 
▪ If platelets remains <math>< 100,000</math> cells/mm^3 14 days after first report of Grade 3 PLT decrease, discontinue study treatment
 
 
Second Episode: Hold alisertib administration and check platelet counts within 5-7 days of report of Grade 1 ANC results of ANC recheck #1
 
(a) results of PLT recheck #1
 
 
▪ If platelets <math>\geq 100,000</math> cells/mm^3, resume alisertib at current dose
 
▪ If platelets <math>< 100,000</math> cells/mm^3, continue to hold alisertib and re-check platelet counts again within the next 7 days but at most 14 days after the first report of Grade 3 PLT (PLT recheck #2)
 
 
(b) results of PLT recheck #2
 
 
▪ If platelets <math>\geq 100,000</math> cells/mm^3, resume alisertib at first dose level below at current dose
 
▪ If platelets remains <math>< 100,000</math> cells/mm^3 14 days after first report of Grade 3 PLT decrease, discontinued 14 days after first report of Grade 3 ANC, discontinue study treatment
 
 
Third Event: Discontinue all study treatment (see note*)
 
*NOTE: If patient is deriving benefit from study treatment and event can be managed safely, consult Study Chair regarding continuation.

	Platelet count decreased Grade 4 ( $< 25,000$ /mm  ) or Grade 3 with bleeding	
Discontinue all study treatment*
 
*NOTE: If patient is deriving benefit from study treatment and event can be managed safely, consult Study Chair regarding continuation.

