Investigations	Neutrophil count decreased Grade 3 or 4 (neutrophils <1000 cells/mm  )	Omit Cycle 1 Days 15-17 administration of alisertib Administer fulvestrant loading dose Check neutrophil count on Cycle 2 Day 1
----------------	--	---

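### Sections 6.4.4, 7.1.3, 7.2 and 7.3 do not agree on when severe neutropenia ends treatment, and the 30-day rule that 6.4.4 cites is not in 7.3

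*Combined protocol and SAP*

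**What the plan says.** Five places in the protocol bear on how long treatment may be held for severe neutropenia.

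- **Section 6.4.4** lists a delay of more than 21 days among the criteria for ending all protocol therapy. Its only exception is "recovery from Cycle 1 Day 15 severe neutropenia where treatment delay of >30 days triggers treatment discontinuation", for which it refers the reader to Section 7.3.
- **Section 7.3** covers events found on Cycle 1 Day 15 and on Day 15 of the first crossover cycle. It has one row, for neutrophils below 1000: omit alisertib on Days 15-17, give the fulvestrant loading dose, and "Check neutrophil count on Cycle 2 Day 1".
- **Section 7.2** (the table for events before each cycle) requires a hold, a first recheck at 5-7 days and a second no later than 14 days after the first report. If the count is still below 1500, the Grade 3 row ends with "14 days after first report of Grade 3 ANC, discontinue study treatment" and the Grade 4 row with "14 days after first report of Grade 4 ANC, discontinue study treatment". Both carry a note that the Study Chair may be consulted on continuation if the patient is benefiting and the event is manageable.
- **Section 7.1.3** stops treatment held for more than 21 days "without resolution of any adverse events other than severe neutropenia", with the same note.
- **Section 6** (opening bullets) refers any interruption of 21 days or more to the Study Chair.

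In the same 7.2 table, the Grade 3 platelet row tells sites to "check neutrophil counts within 5-7 days of report of Grade 3 PLT". It ties the second episode to a report of Grade 1 neutrophil decrease. Every result line in that row is a platelet count.

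**The concern.** A site with a severely neutropenic patient has to know on which day the hold becomes a discontinuation. The protocol gives 14 days in one place and 30 in another, and in a third it exempts the event from a 21-day limit without saying what replaces it. The section cited as the source of the 30-day rule does not contain that rule.

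This touches the primary endpoint because of how response is defined. Section 17.1.1 counts a patient as a responder only if CR or PR is seen on two consecutive evaluations about 8 weeks apart during treatment, and divides by all patients who started. Section 7.1.2 ends fulvestrant when alisertib is discontinued for intolerability. A patient taken off early therefore stays in the denominator and cannot become a confirmed responder, while a patient in the same condition whose site reads another section may still do so.

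**Working it through.** No sample size or power figure is involved. The check sets the clauses side by side and counts days on the nominal 28-day cycle of Sections 6.1 and 6.2.

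**Step 1: is the cited rule in 7.3?** Section 7.3 contains the three instructions listed above and nothing else. It has no delay limit, no discontinuation rule, and no instruction on what to do with the Cycle 2 Day 1 result.

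**Step 2: a Cycle 1 Day 15 event.** Number days from the start of Cycle 1, so the event is on Day 15 and Cycle 2 Day 1 is Day 1 + 28 = Day 29. The interval is 29 − 15 = 14 days. The limits are 14 days (7.2) and 30 days (6.4.4). Neither section says whether the clock for a Day 15 event starts on Day 15 or when Cycle 2 falls due, so all four combinations are shown.

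| 7.2 clock starts | 6.4.4 clock starts | 7.2 limit | 6.4.4 limit | Gap (days) |
|---|---|---|---|---|
| Day 15 | Day 15 | 15 + 14 = 29 | 15 + 30 = 45 | 16 |
| Day 29 | Day 29 | 29 + 14 = 43 | 29 + 30 = 59 | 16 |
| Day 29 | Day 15 | 43 | 45 | 2 |
| Day 15 | Day 29 | 29 | 59 | 30 |

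No combination gives agreement on the nominal schedule. The cycle window of ±3 days would let the third row coincide if Cycle 2 Day 1 fell on Day 31 (31 + 14 = 45), but only by accident of scheduling.

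**Step 3: the recheck at Cycle 2 Day 1.** Suppose 7.2 is read as not reaching back to a Day 15 event. A count below 1000 on Cycle 2 Day 1 is then a first report under 7.2 and leads to a hold. A count of 1000-1499 is below the 1500 recovery level but meets the entry criterion of neither neutropenia row, so no row-specific instruction applies.

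**Step 4: severe neutropenia in a later cycle, count still below 1500.**

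| Hold day | 7.2 | 6.4.4 | 7.1.3 |
|---|---|---|---|
| Day 14 | stop by default | no stop yet | no stop |
| Days 15-21 | already stopped by default | no stop yet | no stop |
| Day 22 on | already stopped by default | stop | exempt, no limit given |

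The exemption in 7.1.3 covers any cycle. The one in 6.4.4 covers only the Day 15 event.

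**Step 5: reach into the endpoint.** Scans are due at the completion of Cycles 2, 4, 6 and so on (Sections 11.1 and 11.2). The first is nominally 2 × 28 = 56 days after the start of treatment and the confirming one 4 × 28 = 112 days. A patient discontinued under the earliest limit in Step 2 (Day 29) leaves treatment before the first scheduled response scan.

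**The case against.** The best defence is that 7.2 is the specific rule and the delay criterion in 6.4.4 a general outer limit. The 6.4.4 list is introduced as inclusive, it separately names unacceptable adverse events, 6.4.2 points to Section 7, and nothing in 6.4.4 orders a site to keep a patient on treatment. This stands for anemia and for Grade 3 platelets, where 14 days sits inside 21. A reader might infer that the rules conflict for every low blood count; the documents do not support that. The defence fails for the Day 15 event, because there 6.4.4 is itself event-specific and its limit is the longer one. No order of precedence is stated.

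A related defence is that the exemption in 7.1.3 simply defers to the neutropenia rows of 7.2. That is a fair reading, but 7.1.3 does not say so, and it leaves the differing scope of the two exemptions unexplained.

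The Study Chair note also counts. Under 7.2 and 7.1.3 a stop is a default, and Section 6 gives the Study Chair a role from 21 days. This softens the contradiction without removing it. The note applies to patients deriving benefit, yet on Cycle 2 Day 1 the first scheduled response scan is still a cycle away, and 6.4.4 carries no such note.

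A reader might also infer that any patient below 1500 on Cycle 2 Day 1 is discontinued under 7.2 and kept under 6.4.4. That holds only if the 7.2 clock runs from Day 15, which the text does not settle: the 7.2 stop presupposes rechecks that 7.3 does not require.

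Finally, the platelet row is plainly a drafting slip. It labels the test as a platelet recheck and acts only on platelet values, so many sites will read through it. It still names the wrong test and the wrong trigger.

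**Conclusion.** The text is wrong as written for severe neutropenia. The rule cited by 6.4.4 is absent from 7.3, the two exemptions cover different patients, and the 14-day and 30-day limits for a Day 15 event differ by 16 days from a shared start and by 2 days in the closest combination. These figures assume the nominal 28-day cycle and that the 7.2 limit reaches a Day 15 event at all. If it does not, the gap is instead a missing instruction for the recheck result. The Grade 3 platelet row is a separate and smaller error.

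Two stronger conclusions are tempting and not supported. One is that this is the toxicity that suspended the trial. Section 3.8 reports that 5 of 12 patients had a Grade 4 toxicity or died on treatment, and the text available for review does not name neutropenia as the cause. The other is that the ambiguity could swing the primary result. The success rule in 17.2 is a difference of at least 4 responses between arms of 45, and the unclear limits apply to both arms. A shift would need an imbalance among patients who would otherwise have responded. No Day 15 neutropenia rate is given, so neither the number affected nor any between-arm effect can be stated. What can be said is that sites reading different sections could handle the same patient differently.

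**What to change.** Reconcile Sections 6.4.4, 7.1.3, 7.2 and 7.3 so that:

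- severe neutropenia has one consistent hold limit for each situation (Cycle 1 Day 15, first crossover Day 15, later cycles);
- the day on which the clock starts is defined;
- the order of precedence between Section 6.4.4 and Section 7 is stated;
- the rule cited by 6.4.4 is either placed in 7.3 or the citation is removed, and 7.3 says what follows from the Cycle 2 Day 1 result.

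Reconcile the test and the second-episode trigger in the Grade 3 platelet row with that row's own platelet results. The clinical team must choose the limits; none is proposed here.

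The cost is protocol wording in an amendment. The design, sample size and analysis do not change.

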- 6.4.6 A patient is deemed *ineligible* if at the time of registration, the patient did not satisfy each and every eligibility criteria for study entry.
- If the patient never received any study treatment, on-study materials (with the exception of biospecimens) must be submitted. No further follow-up is required.
  - If the patient is receiving study treatment at the time the ineligibility is discovered, the patient may continue on study at the discretion of the treating physician as long as there are no safety concerns, and the patient was properly registered. All protocol procedures must be followed. Otherwise, the patient enters the event monitoring phase of the study.
- 6.4.7 If protocol requirements regarding treatment in Cycle 1 of the initial therapy are severely violated to the point the Study Team finds that the patient is not evaluable for primary end point, the patient will be flagged in to study database as a protocol violation. The patient may continue on study at the discretion of the treating physician as long as there are no safety concerns, and the patient was properly registered. All protocol procedures must be followed. Otherwise, no further follow-up is required.
- 6.4.8 If a patient withdraws consent prior to receiving any study treatment or is found to have unacceptable liver enzyme levels [either (1) total bilirubin >1.5 x ULN or (2) alanine transaminase >5 x ULN] on Cycle 1 Day 1 and does not receive protocol treatment, the patient will be deemed a *cancel*. On-study material (with the exception of biospecimens) and the End of Active Treatment/Cancel Notification Form must be submitted. For patients who are cancelled due to unacceptable liver enzyme levels on Cycle 1 Day 1. A comment should be added to the CRF stating that the patient had unacceptable liver enzyme levels on Cycle 1 Day 1 and did not start treatment. No further data submission is necessary.

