#### 8.1.8 **Drug procurement and ordering:**

Open-label alisertib will be provided free of charge to patients by Takeda/Millennium Pharmaceuticals, Inc.

Each institution will order the drug through drug suppliers. (See Pharmacy Manual for order form.)

NOTE: Local drug destruction may occur if the site provides a copy of their local drug destruction policy to the sponsor (Mayo Clinic) and the respective drug suppliers (Takeda/Millennium).

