### 12.1 Definitions

Evaluable for toxicity: All patients will be evaluable for toxicity from the time of their first treatment with alisertib.

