### 17.1 Assessing the impact of adding fulvestrant to alisertib

#### 17.1.1 Primary Endpoint

The primary endpoint is tumor response rate with initial treatment. That is,

- Arm 1: Tumor response rate is defined as 100% times the number of patients who meet the criteria for CR or PR (using RECIST criteria version 1.1) on 2 consecutive evaluations approximately 8 weeks apart during treatment with alisertib monotherapy divided by the number of patients who started alisertib monotherapy.
- Arm 2: Tumor response rate is defined as 100% times the number of patients who meet the criteria for CR or PR (using RECIST criteria version 1.1) on 2 consecutive evaluations approximately 8 weeks apart

during treatment with combination of alisertib and fulvestrant divided by the number of patients who started treatment with the combination of alisertib and fulvestrant.

The study will test the hypothesis that the addition of fulvestrant to alisertib will increase the tumor response rate over that of alisertib alone by at least 20%.

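### Section 6.4.7 lets a treated patient be called unevaluable for the primary endpoint and leave follow-up, which does not fit the 17.1.1 denominator or the follow-up rules in 6.4.4 and 6.4.6

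*Combined protocol and SAP*

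**What the plan says.** Section 6.4.7 covers patients whose Cycle 1 initial treatment departs from the protocol so badly that "the Study Team finds that the patient is not evaluable for primary end point". The stated consequence is that "the patient will be flagged in to study database as a protocol violation". Whether she stays on study is left to the treating physician. If she does not stay, the text is "Otherwise, no further follow-up is required".

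Section 17.1.1 defines the tumor response rate in each arm. Responders are patients with CR or PR on two consecutive evaluations about 8 weeks apart during initial treatment. The Arm 1 count is "divided by the number of patients who started alisertib monotherapy", and the Arm 2 count is "divided by the number of patients who started treatment with the combination of alisertib and fulvestrant". Neither denominator has an exception.

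The only evaluability definition in Section 12.1 concerns safety: "All patients will be evaluable for toxicity from the time of their first treatment with alisertib". Section 12.1 has none for response.

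Section 6.4.4 sends patients who stop protocol therapy for any reason on its list to event monitoring. Section 6.4.6 sends a treated patient later found ineligible to event monitoring if she does not continue.

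**The concern.** The 17.1.1 definition leaves no room for a treated patient who cannot be evaluated. Without two consecutive responding evaluations she is a non-responder. Section 6.4.7 names a category that this definition does not have, and no passage says how its members are analysed.

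The judgement has few safeguards. The degree of violation that triggers it is not defined, no deadline is set, and no independent or blinded review is described. Section 8.1.8 says "Open-label alisertib will be provided free of charge to patients", fulvestrant is an injection given in one arm only, and no blinding appears anywhere in the plan. Section 17.5.1 has the study chair and statistician review the data every 3 months. That the judgement could be made with knowledge of arm and outcome is an inference from these facts, but nothing in the plan prevents it.

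The follow-up sentence matters more, because it is an instruction that sites can carry out as it stands. Progression-free survival (17.1.2.3) runs from randomization to progression or death, and 17.4.1 also estimates overall survival. A patient released from follow-up after a Cycle 1 violation contributes little to either, and the reason for her early censoring is a judgement made after randomization.

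**Working it through.** **1. Reproduce the design (17.2).** Inputs: 28 per arm at the interim, stop if the difference in responses is one or fewer; 45 per arm at the end, success if the combination has at least 4 more responses; response rates 20% and 40%; one-sided alpha 0.15; power 85%. Let D1 be the difference (combination minus alisertib alone) in the first 28 per arm, and D2 the difference in the remaining 45 − 28 = 17 per arm. Then

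P(success) = sum over d ≥ 2 of P(D1 = d) × P(D2 ≥ 4 − d).

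The exact binomial results are 0.1466 at 20% against 20% and 0.8501 at 40% against 20%. The plan's figures stand, and the design works with all treated patients counted.

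**2. Effect of leaving out non-responders without replacement.** The documents give no expected number of 6.4.7 cases, so three in one arm is an assumption for illustration.
- All counted: 9/45 = 20.0% against 12/45 = 26.7%. The rates differ by 6.7 points and the counts by 12 − 9 = 3.
- Three combination non-responders left out: 12/42 = 28.6%. The rates differ by 8.6 points and the counts still by 3.

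The reported combination rate rises by 28.6 − 26.7 = 1.9 points. The success rule is a count, 3 is less than 4, and the trial fails either way. The futility rule is also a count and is equally unaffected.

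**3. What could move the decision.** Either a responder would have to be left out, or patients left out would have to be replaced by others who might respond. Section 6.4.7 provides for neither. Section 17.2 replaces patients who cancel before starting treatment and patients found ineligible. It does not list 6.4.7 cases.

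**4. Follow-up rules side by side, for treated patients who do not continue.**
- Stops for toxicity, delay, own request or another listed reason (6.4.4): event monitoring.
- Found ineligible (6.4.6): event monitoring.
- Eligible, flagged for a Cycle 1 violation (6.4.7): follow-up may end.

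Sections 6.4.6 and 6.4.7 use the same continuation sentence ("the patient may continue on study at the discretion of the treating physician as long as there are no safety concerns") and part only in what follows if she does not continue. An eligible violator can therefore be followed less than an ineligible patient. The rules can also collide: a flagged patient who stops at her own request falls under both 6.4.4 and 6.4.7, with opposite instructions.

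**5. Size of the data loss.** Each patient released is 1/45 = 2.2% of an arm for progression-free and overall survival; three would be 3/45 = 6.7%.

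**The case against.** The strongest reply is that 6.4.7 orders nothing beyond a flag. Section 17.1.1 is the only text that defines the primary analysis, it has no exception for flagged patients, and so it should govern. A patient who continues must follow all protocol procedures. The primary endpoint counts responses during treatment, so ending follow-up after treatment cannot alter it. The clause is confined to Cycle 1 violations, and few patients are likely to meet it.

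Much of this stands. Loss of follow-up is permitted, not automatic, and the secondary time-to-event endpoints bear it. But no precedence between the sections is stated, and an analyst would still find treated patients labelled unevaluable for the endpoint under analysis. Giving 17.1.1 precedence would also leave the follow-up sentence as it is.

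A reader might infer three stronger things that the documents do not support:
- That flagged patients are removed from the denominator. The text does not say so.
- That the clause can reverse the trial's decision. Striking out one documented Arm 1 responder would raise type I error at 20%/20% from 0.147 to about 0.19 (after the interim) or 0.22 (before it), but no passage provides for that.
- That those flagged would be selected by toxicity. Toxicity-driven holds, reductions and the Cycle 1 Day 15 omission are actions laid down in Section 7, so taking them is compliance. The documents do not link violations to toxicity.

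**Conclusion.** The point holds as an unreconciled conflict with a definite but limited consequence. The unevaluable label does not fit the 17.1.1 denominator. The follow-up sentence is out of line with 6.4.4 and 6.4.6 and, if applied, loses survival-type data on eligible, treated, randomized patients. For the primary endpoint the exposure is to the reported rate, 1.9 points in the three-patient example, and the success decision is untouched unless rules that are not in the plan were applied. The size rests on an assumed number of cases, since the documents give none. It should be corrected, because the correction is specific and leaves the design as it is.

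**What to change.** Amend Section 6.4.7 as follows:
- Delete the wording that makes a patient unevaluable for the primary endpoint, and keep the protocol-violation flag.
- Replace the closing follow-up sentence with entry to event monitoring, as in 6.4.6.
- State that flagged patients who started assigned treatment stay in the 17.1.1 denominator, count as non-responders unless a confirmed response is documented, and are not replaced.
- State that any analysis excluding violators is supportive only, with exclusion criteria fixed in advance and applied without knowledge of arm or response.

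The cost is an amendment to the wording, routine event monitoring for a few patients, and possibly a slightly lower response rate than an analysis that left them out. With every treated patient counted, 45 per arm still gives an exact type I error of 0.1466 and power of 0.8501, so no sample size change is needed.
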